5.3.6 Other Considerations

5.3.6.1 Total number of joints

For the calculation of the total number of joints that are tender/swollen, if any joints are not evaluable, the score is prorated by taking the number of joints that are tender/swollen divided by the number of evaluable joints and multiplied by the target number of joints, rounded to nearest integer. If assessment of joints are "Not Done", the joints will be handled as tender and swollen.

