9.5.1.3.1 ASSESSMENT OF TENDER AND SWOLLEN JOINT COUNTS

The number of tender joints and the number of swollen joints will be evaluated during the Screening and Observation Phases, Treatment Phase (Weeks 2, 4, 8, 12, 16, 20, and 24), Extension Phase (up to Week 104, every 4 weeks), and at discontinuation. As a general rule, assessments will be performed by the same investigator or subinvestigator at each site.

A total of 68 joints will be examined for tenderness by applying pressure to the joint or by moving joints. Tender joints will be marked with tick or cross in corresponding frames of the Assessment Sheet for Tender and Swollen Joint Counts (Appendix 7). A total of 66 joints (minus 2 hip joints) will be examined for swollen joints. Swollen joints will be marked with open circles in corresponding frames of the Assessment Sheet for Tender and Swollen Joint Counts (Appendix 7). If assessment cannot be made because the subject had a joint replacement procedure or due to any other reasons, a filled square will be entered.

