5.1 Study Endpoints

5.1.1 Primary Endpoint

- ACR20 response rate at Week 12

The ACR20 response is defined as if the following 3 criteria (ACR components) are met:

1. Greater than or equal to 20% reduction from baseline in the TJC in 68 joints (TJC68)
2. Greater than or equal to 20% reduction from baseline in the SJC in 66 joints (SJC66)
3. Greater than or equal to 20% reduction from baseline in at least 3 of the following 5 assessments:
 - Physician's Global Assessment of Disease Activity (VAS)
 - Patient's Global Assessment of Disease Activity (VAS)
 - Patient's Assessment of Pain (VAS)
 - HAQ-DI
 - CRP

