8 DEFINITIONS AND CONVENTIONS FOR DATA HANDLING

8.1 Baseline, Time Windows for statistical analyses

8.1.1 Definition of baseline value

The baseline value was defined as the most recent value reported just before first dosing.

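### Scoring 'Not Done' joints as tender and swollen at baseline as well as later can create a false fall in the joint counts and falsely meet the two joint-count criteria of ACR20

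*SAP*

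**What the plan says.** SAP 5.3.6.1 has two rules for joints without a result. The first is that "if any joints are not evaluable, the score is prorated": affected joints divided by evaluable joints, times the target number, rounded to an integer. The second covers joints whose assessment is Not Done: "the joints will be handled as tender and swollen". The second rule names no visit, and nothing else in the SAP limits it to visits after baseline.

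SAP 8.1.1 sets the reference value: "The baseline value was defined as the most recent value reported just before first dosing". It asks for no completeness of the joint examination.

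SAP 5.1.1 defines ACR20 by three criteria, all required: a fall of at least 20% in TJC68, the same in SJC66, and "Greater than or equal to 20% reduction from baseline in at least 3 of the following 5 assessments". ACR50 and ACR70 use the same structure (SAP 5.1.2).

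Protocol 9.5.1.3.1 tells the site that if a joint cannot be assessed because of a replacement or "due to any other reasons, a filled square will be entered". Neither document says how Not Done differs from not evaluable.

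**The concern.** Counting a missing joint as affected is a familiar worst-case convention, but it is conservative only on the follow-up side of a comparison. On the baseline side it raises the value from which the fall is measured. A joint that was merely skipped before dosing, and is found normal later, then counts as a joint that recovered. If it was neither tender nor swollen, it inflates TJC68 and SJC66 together, and these are the two counts that every ACR threshold requires to fall.

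The same baseline enters the TJC and SJC changes. If the joint is one of the 28, it also enters DAS28, SDAI, CDAI and EULAR response. It carries into every later visit for that subject. The observed-case, LOCF and non-responder approaches in SAP 5.3.5 do not remove it, because the baseline count looks complete.

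**Working it through.** The plan gives no figure on this point. Its only figures tied to ACR20 are the powers in Protocol 9.7.2 (50 per arm, one-sided 0.0125, chi-square). They reproduce: 91.1% for 30% v 65% and 79.1% for 30% v 60%. The point does not depend on them.

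**Inputs.** The scoring and prorating rules are from SAP 5.3.6.1, the baseline definition from SAP 8.1.1 and the thresholds from SAP 5.1.1 and 5.1.2. The entry minimum of 6 tender and 6 swollen joints is from Protocol 9.3.1. The frequency of Not Done joints is not given.

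**1. False fall.** Let n joints be truly affected at both visits. Let k unaffected joints be Not Done at baseline only.

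- Scored baseline = n + k; later count = n; apparent fall = k/(n + k).
- A 20% fall needs k ≥ n/4, a 50% fall k ≥ n, and a 70% fall k ≥ 7n/3.
- Prorated baseline = n/(68 − k) × 68, rounded. The 66-joint count gives the same integers in these cases.

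| n | k | Baseline, current rule | Apparent fall | Prorated baseline | Apparent fall |
|---|---|---|---|---|---|
| 6 | 2 | 8 | 2/8 = 25.0% | 6/66 × 68 = 6.18 → 6 | 0% |
| 10 | 3 | 13 | 3/13 = 23.1% | 10/65 × 68 = 10.46 → 10 | 0% |
| 12 | 3 | 15 | 3/15 = 20.0% | 12/65 × 68 = 12.55 → 13 | 1/13 = 7.7% |
| 16 | 4 | 20 | 4/20 = 20.0% | 16/64 × 68 = 17 | 1/17 = 5.9% |
| 20 | 5 | 25 | 5/25 = 20.0% | 20/63 × 68 = 21.59 → 22 | 2/22 = 9.1% |

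Both counts must pass, so the larger of the tender and swollen counts decides how many skipped joints are needed. At n = 6, the ACR50 joint thresholds need 6 skipped joints and the ACR70 thresholds need 14. ACR20 is the realistic exposure.

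**2. Worsening can be hidden.** With 12 affected joints and 6 Not Done at baseline, the scored baseline is 18. A later true count of 14 reads as (18 − 14)/18 = 22.2% improvement. The true change is (14 − 12)/12 = 16.7% worsening.

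**3. After baseline the sign reverses.** A true fall from 10 to 8 (20%) with 1 unaffected joint Not Done at the later visit reads as 10 to 9 (10%) and fails.

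**4. Same joints missing at both visits.** Take a true fall from 12 to 6 (50%) with 3 unaffected joints Not Done each time.

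- Current rule: 15 to 9, 6/15 = 40%.
- Prorated at both visits: 13 to 6 (6/65 × 68 = 6.28 → 6), 7/13 = 53.8%.
- Prorated at baseline, worst case later: 13 to 9, 4/13 = 30.8%.

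The split rule does worse here than the current one.

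**5. Illustration only, if a Week 12 test used the rule.** Assume that 1% to 5% of non-responders in both arms become false responders. Then 30% v 60% becomes 30.7% v 60.4% (0.30 + 0.01 × 0.70; 0.60 + 0.01 × 0.40), up to 33.5% v 62.0%. The difference shrinks from 30 to 29.7 and then 28.5 points, and power falls from 79.1% to 78.1% and then 73.8%.

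**The case against.** The strongest reply is that worst-case scoring of an omitted assessment is a deliberate conservative convention. Through Week 84 there is one baseline against 22 scheduled later joint assessments (7 in the Treatment Phase and 15 from Week 28 to Week 84). Joint counts are also needed for eligibility at Screening and Observation, so a wholly missing baseline examination is unlikely. All of that stands, and it limits the realistic case to a few skipped joints. It does not make the rule right at baseline.

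Three stronger readings are tempting, and the documents do not support them.

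- **A reader might infer that a subject with no real change becomes an ACR responder.** The rule touches only two of three required criteria. The third, at least 20% improvement in 3 of 5 other measures, does not use joint counts. The subject at risk is one who passes those measures but not the joint criteria.
- **A reader might infer that the Week 12 primary result is compromised, or tilted toward E6011.** SAP section 3 says that this document covers the Extension Phase, and SAP 5.4.1 plans no primary efficacy analysis. The Treatment Phase SAP is not among the documents, so it cannot be told whether the same rule applies there. Baseline also precedes dosing in a blinded trial, so skipped joints should not differ systematically by arm. Step 5 shows that equal misclassification dilutes the difference.
- **A reader might infer that the filled square and Not Done are one situation under two opposite rules.** The square may map to not evaluable, with Not Done a separate CRF status for an omitted assessment. The CRF and the joint assessment sheet are not available. What can be said is that Not Done is undefined.

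**Conclusion.** The concern holds in a limited form. Followed as written, SAP 5.3.6.1 inflates the baseline TJC68, SJC66 and 28-joint counts when unaffected joints are Not Done before dosing. If those joints are examined later, no change reads as a fall of k/(n + k). Two skipped joints are enough at the entry minimum of 6, three at 10 and five at 20, to pass the 20% joint criteria. A false ACR20 still needs the third criterion to be met.

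This rests on three assumptions: the unrestricted wording includes baseline, the skipped joints are truly neither tender nor swollen, and they are examined at the later visit. The outputs affected in this SAP are descriptive summaries and displays by visit. How many subjects are affected cannot be judged without the number of Not Done joints by visit and arm. The rule should be corrected, but the documents do not show that any reported result is wrong.

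**What to change.** In SAP 5.3.6.1, replace the Not Done sentence with one that prorates these joints over the assessed joints, exactly as for not-evaluable joints, at baseline and at all later visits. State in the same place what Not Done means and how it relates to the filled square.

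Do not adopt prorating at baseline with worst-case scoring afterwards as the main rule, because step 4 shows that it can understate a real improvement more than the current rule does. Worst-case scoring after baseline may be kept as a sensitivity analysis.

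Tabulate Not Done joints by visit and treatment group. If there are none at baseline, saying so closes the baseline concern. Confirm also whether the Treatment Phase SAP carries the same rule.

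The cost is one sentence, a small programming change and one table. The downside is that counts rest on fewer joints when several are missing, and prorating with rounding can leave a small residual error: 12 positive with 3 unassessed gives 13, a 7.7% apparent fall, against 20% now.

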5.3.6.2 HAQ subcategory score

The HAQ-DI is composed of 20 items in 8 categories (Dressing and Grooming, Arising, Eating, Walking, Hygiene, Reach, Grip, Activities). To calculate the HAQ-DI, the highest sub-category score determines the value for each category, there must be responses in at least 6 of the 8 categories or else a HAQ-DI cannot be computed. The category scores are then averaged into an overall HAQ-DI.

HAQ-DI = (Amount of score with all categories) / (Number of categories scored)

5.4 Efficacy Analyses

The FAS will be used for the efficacy analyses.

5.4.1 Primary Efficacy Analyses

No primary efficacy analyses are planned for analyses for extension phase.

5.4.2 Secondary Efficacy Analyses

For each component of ACR (TJC, SJC, VAS [patient's assessment of pain, patient's global

assessment of disease activity and physician's global assessment of disease activity], functional assessment by subjects (HAQ) and CRP·ESR), DAS28-ESR, DAS28-CRP, SDAI, and CDAI in each visit, the values and the changes from baseline will be summarized by treatment group.

For mTSS, values and changes from baseline will be summarized by treatment group. For DAS28-ESR and DAS28-CRP, frequency and percentage of each classification (no response, moderate response, good response) by EULAR response criteria will be summarized by treatment group and visit in a shift table. For DAS28-ESR, DAS28-CRP, SDAI and CDAI, frequency and percentage of each category (Remission, Low, Moderate, High) will be summarized by treatment group and visit in a shift table.

The mean change from baseline of ACR components, DAS28-CRP, DAS28-ESR, CDAI and SDAI - visit will be displayed by treatment group. ACR response rate - visit will be displayed by treatment group. Cumulative probability of the change from baseline in mTSS will be displayed at week 52 and Week 76.

All efficacy endpoints for the treated subjects will be listed.

5.4.3 Other Efficacy Analyses

No other efficacy analyses are planned for this study.

5.5 Pharmacokinetic, Pharmacodynamic, Pharmacogenomic, and Other Biomarker Analyses

5.5.1 Pharmacokinetic Analyses

Serum E6011 Concentration

Serum PK samples for PK analyses will be collected on Week 0 (predose), Week 1 (predose), Week 2 (predose), Week 4 (predose), Week 8 (predose), Week 12 (predose) , Week 16 (predose), Week 20 (predose), Week 24 (predose) to Week 104 (predose) by 4 Weeks.

The Safety Analysis Set will be used for PK analyses.

No Tables are planned for analyses for extension phase.

<Listing>

Actual sampling time and serum concentrations of E6011 for each subject will be listed.

<Figure>

No figures are planned for analyses for extension phase.

5.5.2 Pharmacodynamic, Pharmacogenomic, and Other Biomarker Analyses

5.5.2.1 Pharmacodynamic, Pharmacogenomic Analyses

No Pharmacodynamic and Pharmacogenomic analyses are planned for this study.

5.5.2.2 Other Biomarker Analyses

All biomarker analyses will be performed using the Full Analysis Set.

For the Extension Phase, summary statistics for serum RF concentration, serum anti-CCP antibody concentration, and serum matrix metalloproteinase-3 concentration, serum tartrate resistant acid phosphatase 5b (TRACP-5b) concentration, serum cytokine concentration, serum leucine-rich alpha-2 glycoprotein 1 (LRG1) concentration, serum angiopoietin 2 (Ang2) concentration, Vectra™ DA and its component (vascular cell adhesion molecule-1 (VCAM-1), epidermal growth factor (EGF), vascular endothelial growth factor (VEGF)-A, interleukin (IL)-6, tumor necrosis factor receptor-I (TNF-RI), serum matrix metalloproteinase-1, serum matrix metalloproteinase-3, YKL-40, leptin, resistin, SA and CRP) value, change from baseline and percent change from baseline, by treatment group and time point, will be calculated. Exploratory investigations of the relationship between efficacy and biomarkers will be conducted. The analysis plan for CX3CR1 is out of scope of this document. All other biomarkers will be collected on baseline and postbaseline, referring [section 8.1.3](#) "Time window".

Subject data listings will be provided.

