2 CLINICAL PROTOCOL SYNOPSIS

Compound No.: E6011
Name of Active Ingredient: To be determined
Study Protocol Title
A Dose Response Study of E6011 in Subjects With Rheumatoid Arthritis Inadequately Responding to Methotrexate
Study Regions (Countries) or Sites
Japan
Study Period and Phase of Development
October 2016 to February 2020 (planned) Phase 2
Objectives
To conduct the following assessments on repeated subcutaneous administrations of E6011 in rheumatoid arthritis (RA) patients inadequately responding to methotrexate (MTX):
<Primary objectives>

 • To evaluate the efficacy of E6011 compared with placebo by using ACR20 response rate at Week 12 as a primary endpoint • To evaluate the safety and tolerability of E6011
<Secondary objectives>

 • To evaluate the effect of E6011 on suppressing radiographic progression of joint destruction at Week 24 • To evaluate the pharmacokinetics (PK) and immunogenicity of E6011
<Exploratory objective>

 • To explore the PK/pharmacodynamics (PD) and biomarkers of E6011
Study Design
This study is a multicenter, randomized, double-blind, placebo-controlled, parallel-group comparison study. The following 4 treatment groups are selected for the study: E6011 100 mg, 200 mg, 400 mg, and placebo. In the E6011 100 mg, 200 mg, and placebo groups, subjects will receive the study treatment (100 mg, 200 mg, or placebo, respectively) at Weeks 0, 1, 2, and then every 2 weeks. In the E6011 400 mg group, subjects will receive 400 mg at Weeks 0, 1, 2, 4, 6, 8, 10 and then 200 mg every 2 weeks.
The study consists of Screening, Observation, Treatment, Extension, and Follow-up Phases.
After undergoing screening assessments within 42 days prior to the study treatment, subjects with the certain eligibility confirmed in the Observation Phase will be allocated to any of the E6011 100 mg, 200 mg, 400 mg, or placebo groups at a 1:2:2:2 ratio through dynamic allocation using the following factors: C-reactive protein (CRP) level at the Screening Phase, disease duration, and history of biologics treatment.
In the Treatment Phase (24 weeks), subjects will receive either E6011 or placebo at Weeks 0, 1, 2, and every 2 weeks until Week 22 in a double-blind manner.

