The last subject entered the Extension Phase (open-label) in March 2018, and all subjects had completed 52 weeks of treatment with E6011 by March 2019. Consequently, it was

considered unnecessary to conduct any non-safety assessments after March 2019, and the protocol will be revised to Version 6.

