9.5.1.4 Pharmacokinetic, Pharmacogenomic, Biomarker, and Immunogenicity Assessments

After the date Version 6 of the protocol is approved by IRB, it is unnecessary to conduct assessments for pharmacokinetic, pharmacogenomic, biomarker, and immunogenicity. However, pharmacokinetic and immunogenicity assessments will be conducted at discontinuation.

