- a. Study drug will be administered upon completion of all the planned investigations (except for injection site findings) on the day.
- b. To measure height only at the Screening Phase and W52.
- c. To examine injection site findings after study drug administration.
- d. To perform pregnancy test in women of childbearing potential. On-site test conducted at the Observation Phase only.
- e. If any postdose abnormality is observed in neurological examination, head MRI (T1-weighted image, FLAIR image, diffusion-weighted image) will be performed within 2 weeks along with consultation to a neurologist.
- f. The interval between study treatments is at least 7 days (at least 6 days between treatments)
- g. Administration of study drug at Week 24 is done in an open-label manner.
- h. W52+2n: W54, 58, 62, 66, 70, 74, 78, 82, 86, 90, 94, 98, 102
- i. W52+4n: W56, 60, 68, 72, 80, 84, 92, 96
- j. Basically performed at study discontinuation, and a missing value is permissible only when collection of the sample is difficult due to abrupt discontinuation.
- k. Will only be conducted if blood sample is judged to be feasible at the visit.
- l. After the date Version 6 of the protocol is approved by IRB, applicable assessments will not be conducted. However, assessments of serum E6011 concentration and serum anti-E6011 antibody will be conducted at discontinuation.

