Immunocytes such as blood CX3CR1-positive cells	5 mL		once	4 times	once ^c	once ^d
Each Phase		52.0 mL	41.8 mL	225.6 mL	591.8 mL	21 mL
Screening to Week 24			319.4 mL			
Screening to Week 104			911.2 mL			
Screening to the Follow-up Phase			932.2 mL			

a: Blood collections for these items (inside the brackets) are included in those for the items just above.

b: The volume of blood sample is 5 mL at the time point for assessing both serum E6011 concentration and serum anti-E6011 antibody and 2 mL at the time point for assessing serum E6011 concentration only.

c: Twice for subjects who discontinue treatment later than Week 52

d: Will only be conducted if blood collection is judged to be feasible at the visit.

Overview of Protocol Amendment between Ver. 5 and Ver. 6

A Dose Response Study of E6011 in Subjects with Rheumatoid Arthritis Inadequately Responding to Methotrexate

(The parts of change: underline)

Protocol body

Pertinent page	Before Amendment (Ver. 5, August 31,2018)	After Amendment (Ver. 6, March 25, 2019)	Reason for Amendment
P7, 2. CLINICAL PROTOCOL SYNOPSIS Concomitant Drug/Therapy P31, 9.4.7.1.2 Restricted Concomitant Drugs	(no text)	
<Restricted Concomitant Drugs>
 
After the date Version 6 of the protocol is approved by IRB, dose reduction, dose interruption, dose increase following the dose reduction (up to the initial dose level), and restarting administration after interruption will be allowed for MTX, folic acid, corticosteroids, or herbal medicine indicated for RA).
 
There will be no restrictions in using NSAIDs (oral, suppository, or topical).
	Because it was considered unnecessary to conduct any non-safety assessments
P8, 2. CLINICAL PROTOCOL SYNOPSIS Assessments	(no text)	
After the date Version 6 of the protocol is approved by IRB, it is unnecessary to conduct assessments other than <safety>.
	Because it was considered unnecessary to conduct any non-safety assessments
P19, 7. INTRODUCTION	(no text)	
The last subject entered the Extension Phase (open-label) in March 2018, and all subjects had completed 52 weeks of treatment with E6011 by March 2019. Consequently, it was considered unnecessary to conduct any non-safety assessments after March 2019, and the protocol will be revised to Version 6.
	Because it was considered unnecessary to conduct any non-safety assessments

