7 CHANGES IN THE PLANNED ANALYSES

Changes in the planned analyses for protocol are as follows:

- Based on the protocol amendment Version 6, all efficacy results will be summarized until week 84.
- Regarding the PK analysis for extension phase, only listing will be created.

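### Version 6 ended biomarker sampling but SAP 5.5.2.2 sets no cut-off, so late biomarker summaries, above all Week 104, would rest on a shrinking part of the cohort; a stated limit and a paired summary fix this cheaply.

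*SAP*

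**What the plan says.** **What stopped.** On Version 6, Protocol 9.5.1.4 says that "it is unnecessary to conduct assessments for pharmacokinetic, pharmacogenomic, biomarker, and immunogenicity" once the IRB has approved it; only PK and immunogenicity are kept at discontinuation. Protocol 9.5.2.1 names the RF/anti-CCP/MMP-3, cytokine/LRG1/Ang2, TRACP-5b and Vectra DA samples. The matching footnote to Protocol Table 4 reads "After the date Version 6 of the protocol is approved by IRB, applicable assessments will not be conducted".

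**How the SAP responded.** SAP 7 states "Based on the protocol amendment Version 6, all efficacy results will be summarized until week 84", and SAP 3 says the same. SAP 5.5.2.3 ends the immunogenicity analysis at Week 84. SAP 5.5.1 and SAP 7 reduce Extension Phase PK to a listing. The joint x-ray windows (SAP Table 8.12) end at Week 76, although the protocol schedules a Week 104 film.

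**Biomarkers.** SAP 5.5.2.2 plans "For the Extension Phase, summary statistics for serum RF concentration, serum anti-CCP antibody concentration, and serum matrix metalloproteinase-3 concentration" and for the remaining markers: value, change and percent change by group and time point. It names no final visit and refers to SAP 8.1.3. There, Table 8.3 (RF, anti-CCP, MMP-3) runs every 4 weeks to Week 104. Tables 8.7 (TRACP-5b, Vectra DA) and 8.9 (cytokines, LRG1, Ang2) have Weeks 52 and 104 as their only Extension Phase visits. SAP 7 does not mention biomarkers.

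**The concern.** The last doses in this trial are spread over many months, so a calendar stop to sampling removes late study weeks from late enrollees and leaves early enrollees complete. A programmer who follows SAP 5.5.2.2 and its windows would produce rows up to Week 104, because no sentence says otherwise. Those rows would stand beside earlier rows that cover nearly everyone still in the study.

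The point bears most on the five markers or panels with only two Extension Phase visits. Their whole late course is Week 52 against Week 104, and the two means would come from different sets of subjects.

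Early and late enrollees are also not fully interchangeable at a given study week. Version 5 (31 August 2018) removed the limit on the number of dose escalations. On that date a subject first dosed on 27 March 2017 was at about Week 75, and the last-enrolled subjects were at about Weeks 46-50.

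**Working it through.** **Inputs from the documents**
- Version 6 date: 25 March 2019 (protocol amendment overview). Site IRB dates are not given.
- Study period: "October 2016 to February 2020 (planned" (Protocol 2). The actual first dose date is not given.
- Last entry to the Extension Phase: "The last subject entered the Extension Phase (open-label) in March 2018" (Protocol 7).

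**Assumptions, not in the documents:** first dose between 1 October and 1 December 2016; uniform accrual; sampling stop between 25 March and 25 May 2019; no dropout; observed cases only (SAP 5.3.5 gives no missing-data rule for biomarkers).

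**Step 1. Week 0 of the last subject.** March 2018 minus 24 x 7 = 168 days gives 14 September to 14 October 2017.

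**Step 2. The SAP's own Week 84.** SAP 3 describes it as the latest visit of ongoing subjects at the amendment. On 25 March 2019 the last subject was at Week 75.3-79.6, and would reach Week 84 between 25 April and 25 May 2019. The figure therefore fits the last-enrolled subject if approval came about 31-61 days after the version date. It cannot be the furthest visit of any subject: someone first dosed in October 2016 reached Week 104 by 29 October 2018 at the latest.

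**Step 3. Who can have a late sample.** Latest Week 0 = stop date minus 7 x week. With a stop on 25 March 2019:
- Week 88: minus 616 days, Week 0 by 17 July 2017
- Week 104: minus 728 days, Week 0 by 27 March 2017

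Each day of approval lag moves these dates one day later.

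**Step 4. Calendar coverage.** Share = (stop date - 7 x week - first dose) / (last Week 0 - first dose), capped at 100%.

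| Week | Coverage |
|---|---|
| 76 | 98-100% |
| 84 | 81-100% |
| 88 | 72-100% |
| 96 | 54-84% |
| 104 | 37-68% |

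Week 104, low end: first dose 1 December 2016, last Week 0 14 October 2017, stop 25 March 2019, so 116/317 = 0.37. High end: first dose 1 October 2016, last Week 0 14 September 2017, stop 25 May 2019, so 238/348 = 0.68.

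If the stop is placed exactly where the last subject reaches Week 84, Week 88 coverage is 90-93% and Week 104 coverage is 51-63%.

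**Step 5. Precision.** The standard error relative to full coverage is 1/sqrt(share): 1/sqrt(0.68) = 1.21 and 1/sqrt(0.37) = 1.64. In the planned 100 mg group of 25, Week 104 has about 0.37 x 25 = 9 to 0.68 x 25 = 17 subjects before dropout.

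**Step 6. The Week 52 window.** Tables 8.7 and 8.9 set the Week 52 base date at +334 days, which is 334/7 = Week 47.7. With 14 days either side and the upper bound excluded, the window is +320 to +347. An on-schedule Week 52 visit is 364 +/- 7, that is +357 to +371, and lies wholly outside. As written, the Week 52 row for these markers would be nearly empty.

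**The case against.** The best defence is that Week 104 is an inference. SAP 5.5.2.2 never names it, and the windows do not fix the reporting horizon: Table 8.3 also reaches Week 104 for joint counts, VAS and HAQ, and Table 8.8 for anti-E6011 antibody, yet both are cut at Week 84 elsewhere. Tables 8.3 and 8.7 also serve safety tests that continued. The table shells are in a separate document. This stands as a caution about intent. It does not close the gap, because the other domains have an overriding sentence and biomarkers have none.

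It is also fair that the summaries are descriptive, serve an exploratory objective, include within-subject change from baseline, and lose subjects for an administrative reason. That limits the harm. Protocol 9.7.1.9 promises Extension Phase biomarker analyses, so keeping collected data is defensible.

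Four stronger readings are tempting and are not supported:
- That all of Weeks 88-104 describe only the earliest enrollees. The loss is gradual, and Weeks 88-100 concern RF, anti-CCP and MMP-3 alone.
- That Week 104 coverage could be as low as 15%, with a 2.6-fold standard error. This needs back-loaded enrolment, and the documents give no accrual curve.
- That the sponsor chose Week 84 to avoid mixing populations. SAP 3 gives only the latest visit of ongoing subjects as the reason.
- That a shift in subject or site mix would show as a drug effect. The documents hold no data on this.

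**Conclusion.** A cheap improvement, not a flaw in a test. As written, nothing ends the biomarker summaries before Week 104, and the Week 104 row can include only subjects first dosed by about 27 March 2017 plus the approval lag. The 37-68% coverage and the 1.2- to 1.6-fold standard error rest on uniform accrual, the assumed first-dose and stop dates, and no dropout; actual enrolment and IRB dates would replace them. The effect is small at Week 88 and material at Week 104. The consequence is a late time course that compares different sets of subjects. For the markers with only two Extension Phase visits, the Week 52 window error must be resolved first, or there is almost nothing to compare.

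**What to change.** 1. In SAP Tables 8.7 and 8.9, correct the Week 52 base date from +334 to +364 days (52 x 7). The window becomes +350 to +377 and contains an on-schedule visit. Other window tables carry the same +334 and should be checked together.
2. In SAP 5.5.2.2, summarise RF, anti-CCP and MMP-3 to Week 84 and list later values.
3. For TRACP-5b, Vectra DA, cytokines, LRG1 and Ang2, keep Week 104 with n shown, and summarise Weeks 52 and 104 in subjects with both samples. A plain Week 84 cut would remove the only visit after Week 52 for these markers.
4. Record the change in SAP 7; Protocol 9.7.5 already provides for documenting SAP revisions in the study report.

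The cost is SAP wording and one paired summary, with no new data. The downside is that late RF, anti-CCP and MMP-3 values appear only in listings, and the paired summary is smaller than an all-available Week 52 row.
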